9. BIOMARKER, CORRELATIVE, AND SPECIAL STUDIES

9.1 Background of exploratory biomarker studies:

The objectives of our exploratory biomarkers are to define the genomic characteristics and the immune microenvironment of leptomeningeal disease in the setting of immune checkpoint inhibitors. Whole-exome sequencing and transcriptome data from non-CNS and CNS metastases and LMD will enable the identification of mutations, insertion/deletion events, and copy-number changes. We also expect to identify genetic signatures that predict response to immunotherapy. Based on our preliminary data across 104 brain metastases, we anticipate that we will identify novel drivers in LMD. We expect to observe changes in RNA/protein expression profiles and identify gene pathways that are consistently and differentially enriched in CSF T cells and myeloid cells by checkpoint blockade. Correlation of clinical outcome with these transcriptomic analyses may lead to predictive signatures of response to immunotherapy. Moreover, we may find evidence of immunosuppression by other pathways, which may suggest new therapeutic strategies for LMD for future investigations. In addition, we may find gene pathways that are enriched in T cells and/or myeloid cells in both the peripheral blood and CSF, which may provide a strategy for immune monitoring of patients on immunotherapy in a more accessible manner. Likewise, we may find changes in cytokines and the proteome in the CSF in response to immunotherapy. If similar cytokines/proteins are altered in the CSF and blood, then such proteins have the potential to serve as biomarkers for responsiveness to immunotherapy.

9.2 Methodology

Whole-exome sequencing: Whole-exome sequencing from tumor and cell-free DNA from CSF and blood will be performed using pipelines that have been tested on several thousand samples at the Broad Institute and described in our recent publications. DNA will be subjected to solution-phase hybrid capture followed by Illumina sequencing to >150x mean coverage. Mutations and allele-specific copy-number changes will be determined within the Firehose pipeline environment at the Broad Institute using a suite of existing tools. The significance of copy-number changes and mutations will be determined using GISTIC and MutSig, respectively, and compared to rates of alterations in the same genes in published large sequencing efforts of unmatched samples. To understand inter- and intratumoral heterogeneity, we will perform an integrative analysis of somatic single nucleotide variants and somatic copy-number alterations. This analysis will allow us to estimate the clonal architecture of the primary and metastatic samples from each patient, and to reconstruct phylogenetic trees relating all of the subclones. For each recurrent mutation, the frequency with which these mutations are present in all or only fractions of cancer cells will be determined.

Transcriptome sequencing and analysis: RNA will be extracted with QIAGEN kits. Non-strand specific RNA sequencing performed at the Broad Institute uses a large-scale, automated variant of the Illumina Tru Seq™ RNA Sample Preparation. This method uses oligo dT beads to select

mRNA from the total RNA sample. The selected RNA is heat fragmented and randomly primed before cDNA synthesis from the RNA template. The resultant cDNA then goes through Illumina library prep (end repair, base 'A' addition, adapter ligation, and enrichment) using Broad designed indexed adapters for multiplexing. After enrichment, the samples will be qPCR quantified and equimolar pooled before proceeding to Illumina sequencing, which is done on the Illumina HiSeq 2000. RNA-seq analysis will be carried out using PRADA (Pipeline for RNA-Sequencing Data Analysis). Somatic variant, small deletions and insertion calling will be performed within the Firehose environment at the Broad Institute with the published caller algorithms.

Cell Purification by Flow Cytometry: CSF will be sorted on CD45 to separate tumor (CD45-) and immune (CD45+) cells for genomic and transcriptomic analyses. CD4⁺ and CD8⁺ T cells and myeloid cells (CD11b⁺) will be purified from the CSF and PBMC by flow cytometry and processed for transcriptome sequencing. We will systematically assess differentially expressed transcripts in pre- and on- treatment samples to determine if there is enrichment within particular gene pathways (such as exhaustion, anergy, senescence) through GeneSet Enrichment Analysis (GSEA) and gene co-expression network analysis.

Cytokine and Proteomic Analyses: We will analyze cytokines in CSF and serum using cytokine bead arrays. High-resolution mass spectrometers and isobaric tandem mass tags will be used to quantify proteins from CSF and serum samples. The tandem mass tag technology allows for the analysis of 6-10 samples within a single experiment. For example, protein expression can be profiled after nine treatment conditions and compared to an untreated sample across >6,000 proteins. All mass spectrometry data will be analyzed in partnership with the Thermo Fisher Scientific Center for Multiplexed Proteomics at Harvard Medical School.

9.3 Collection and Shipping of Tissue Specimen(s)

Collection, Processing and Handling of CSF: One 3 to 10 mL sample of CSF in a clear CSF tube should be collected as per section 10 every three weeks and couriered to the [name] laboratory at the address below within 1 hour of obtaining the sample. Label each tube with (1) sample collection date and time, (2) patient study ID and medical record number, (3) protocol study number, and (4) sample type (e.g., CSF). When a sample is shipped, please page the [name] lab by calling [contact] and ask to page [name] at [name] and [name] at [name].. For any questions or concerns regarding research sample collection or shipment, please contact [name] or [name].

[name] Lab
[name]
[name]
[name]

Collection, Processing and Handling of Archived Specimens: If available, for each resection or prior biopsy 1 FFPE block should be clearly labeled and forwarded to [name] laboratory (at the address below) at Massachusetts General Hospital for molecular testing within 30 days of registration, or surgery happens during trial, within 30 days of surgery or biopsy. If an institution is unable to provide a tissue block, cut 15 unstained slides five-micron sections and mount on charged glass slides. Slides need to be cut with a new blade and using a fresh water bath to avoid contamination. Label the slides with patient ID number, accession number, and order of sections (*include thickness of section if applicable*). For samples containing less than 1 square cm of tumor tissue, multiple sections should be mounted onto each slide to ensure that the appropriate amount of tumor tissue is available. Do not bake or place covers slips on the slide.

Shipping of Tissue Specimen(s): Shipment on Monday through Thursday by overnight service to assure receipt is encouraged. Do not ship specimens on Fridays or Saturdays.

[name]
Massachusetts General Hospital Cancer Center
[name]
[name]

Shipping of Blood Specimen(s): Collect 20 mL of venous blood at pre-registration, 20 mL every 3-4 weeks as per the calendar in section 10. All blood samples should be collected in EDTA anticoagulant vacutainer tubes. The tubes should be inverted approximately 8-10 times to mix the EDTA. Refrigerate (please do not freeze) sample until shipping. The sample should be placed in a biohazard bag and couriered to the [name] laboratory at the address below within 1 hour of obtaining the sample. Label each tube with (1) sample collection date and time, (2) patient study ID and medical record number, (3) protocol study number, and (4) sample type (e.g., blood). When a sample is shipped, please page the receiving lab by calling [contact] and ask to page [name] at [name] and [name] at [name]. For any questions or concerns regarding research sample collection or shipment, please contact [name] or [name].

[name] Lab
[name]
[name]
[name]

10. STUDY CALENDAR

Baseline evaluations are to be conducted within 14 days prior to start of protocol therapy, with the exception of CSF with positive cytology, which must be done \leq 6 weeks prior to initiation of study treatment. Also, if patients received other chemotherapy or targeted therapy within 14 days prior to start of protocol therapy, CBC and serum chemistry (including LFTs and creatinine) should be done within 5 days prior to start of protocol therapy. Scans and x-rays must be done \leq 4 weeks prior to the start of therapy. In the event that the participant's condition is deteriorating, laboratory evaluations should be repeated within 48 hours prior to initiation of the next cycle of therapy.

Assessments must be performed prior to administration of any study agent. Study assessments and agents should be administered within \pm 3 days of the protocol-specified date, unless otherwise noted.

Calendar During Induction Phase for Melanoma, Small Cell Lung Cancer, Breast Cancer, Bladder Cancer, Renal Cancer and Other Solid Tumors

	Pre-Study	Wk 1	Wk 2	Wk 3	Wk 4	Wk 5	Wk 6	Wk 7	Wk 8	Wk 9	Wk 10	Wk 11	Wk 12	Off Study ^h	Follow-up visits ⁱ
Ipilimumab		A			A			A			A				
Nivolumab		B			B			B			B				
Informed consent ^a	X														
Demographics ^a	X														
Medical history ^a	X														
Concurrent meds	X	X-----X													
Physical exam ^b	X	X	X	X	X	X	X	X	X	X	X	X	X	X	X
Vital signs	X	X	X	X	X	X	X	X	X	X	X	X	X	X	X
Height	X														
Weight	X	X			X			X			X			X	X
Performance status	X	X			X			X			X			X	X
CBC w/diff, plts	X	X			X			X			X			X	X
Serum chemistry ^c	X	X			X			X			X			X	X
EKG (as indicated) ^d	X														
Adverse event evaluation		X-----X												X	X
Tumor measurements	X	Tumor measurements are repeated every 6 weeks. Documentation (radiologic) must be provided for participants removed from study for progressive disease.												X	
Radiologic evaluation	X	Radiologic measurements should be performed every 6 weeks (Brain MRI and CT Chest/Abd/Pelvis)												X	X
B-HCG	X ^e							X							X
Cerebrospinal fluid	X ^f	X			X			X			X				
Blood ⁱ	X	X			X			X			X			X	X
Archival tissue ^g	X													X	X

A: For melanoma, small cell lung cancer, breast cancer, bladder cancer and other solid tumors (except NSCLC and head and neck cancers): Ipilimumab 3mg/kg every 3 weeks x 4 doses during induction.. For renal cell cancer: Ipilimumab 1mg/kg every 3 weeks x 4 doses during induction.

B: For melanoma, small cell lung cancer, breast cancer, bladder cancer and other solid tumors (except NSCLC and head and neck cancers): Nivolumab 1mg/kg every 3 weeks for 4 doses during induction. For renal cell cancer: nivolumab 3mg/kg every 3 weeks x 4 doses during induction.

^aAll screening procedures to be performed within 14 days of start of study treatment, with the exception of CSF with positive cytology, which can be 6 weeks prior to initiation of study treatment. C1D1 and Day 1 of subsequent cycles: For C1D1 only, screening assessments may serve as day 1 assessments, except serum pregnancy (within 72 hours of drug) and except in the event that there are any indications that the participant's condition is deteriorating for which laboratory evaluations should be repeated within 48 hours prior to initiation. For all subsequent cycles, required assessments should be performed within 3 days of scheduled cycle day 1.

^bPhysical examination must include neurologic assessment.

^cSerum chemistries: Serum chemistry tests include albumin, amylase, lipase, BUN, creatinine, ALT, AST, LDH, serum alkaline phosphatase, direct and total bilirubin, glucose, total protein, sodium, potassium, chloride, HCO3, calcium, uric acid and TSH. A reflexive free T4 and free T3 will be performed reflexively for out of range TSH values. Patients should also be tested for Hepatitis B virus surface antigens (HBV sAg) and hepatitis C virus ribonucleic acid (HCV antibodies) at screening only.

^dEKG should be obtained at baseline for screening and then as clinically indicated

^eSerum pregnancy test (women of childbearing potential) is required within 72 hours of C1D1 dose. Pregnancy will be performed every 6 weeks while on treatment, and at 30 days and 70 days post last dose of Nivolumab

^fCerebrospinal fluid will be collected every 3 weeks during the induction phase and every 4 weeks during the maintenance phase to assess disease status (will be sent for cell count, protein, glucose, cytology) and 10cc will be saved for correlative studies as described in Section 9.0

^gTissue collected as part of clinical care (e.g. from prior biopsy, craniotomy) will be collected. See Section 9 for specimen collection

^h: Off-study evaluation: End of treatment assessments to be performed within 7 days after last day drug administration or within 7 days after decision to end treatment. Assessments may continue for ongoing reportable adverse events. In participants who discontinue study treatment without documented disease

progression, every effort should be made to continue monitoring their disease status by radiologic imaging every 6 weeks (+/- 7 days) until (1) the start of new anti-cancer treatment, (2) documented disease progression, (3) death or (4) the end of the study, whichever occurs first

ⁱ: Follow-up visit 1 = 30 days from the last dose +/- 7 days or coincide with the date of discontinuation (+/- 7 days) if date of discontinuation is greater than 37 days after last dose, Follow-up visit 2 (FU2) = 8-10 weeks (+/- 7 days) from follow-up visit 1. After 2 followup visits, patients will be followed with a phone call every 10-12 weeks for survival information.

^jBlood will be collected at screening, Day 1, then every 3 weeks during the induction phase and every 4 weeks during the maintenance phase (two 10 mL EDTA/lavender top tube) and at the end of treatment

Calendar During Maintenance Phase for Melanoma, Small Cell Lung Cancer, Breast Cancer, Bladder Cancer, Renal Cancer and other Solid Tumors

	Wk	Wk	Wk	Wk	Wk	Wk	Wk	Wk	Wk	Wk	Wk	Wk	Off Treatment	Follow-up visits ⁱ
	13	14	15	16	17	18	19	20	21	22	23	24		
	To be repeated beyond 24 weeks until patient goes off study													
Nivolumab (for melanoma and renal cell carcinoma)	B			B					B					
Nivolumab (for small cell lung cancer, breast cancer and bladder cancer)	C		C	C		C		C			C			
Concurrent meds	X-----X													
Physical exam ^b	X		X		X		X		X		X		X	X
Vital signs	X		X		X		X		X		X		X	X
Height														
Weight	X		X		X		X		X		X		X	X
Performance status	X		X		X		X		X		X		X	X
CBC w/diff, plts	X		X		X		X		X		X		X	X
Serum chemistry ^c	X		X		X		X		X		X		X	X
EKG (as indicated) ^d														
Adverse event evaluation	X-----X												X	X
Tumor measurements	Tumor measurements are repeated every 8 weeks. Documentation (radiologic) must be provided for participants removed from study for progressive disease.												X	
Radiologic evaluation	Radiologic measurements should be performed every 8 weeks (Brain MRI and CT Chest/Abd/Pelvis)												X	X
B-HCG	X						X							X
Cerebrospinal fluid	X				X				X					
Blood ^j	X				X				X				X	X
Archival tissue ^g													X	X

B: For melanoma, renal cell carcinoma and other solid tumors: Nivolumab 480 mg Q4 weeks during maintenance phase

C: For small cell lung cancer, breast cancer and bladder cancer: nivolumab 240mg every 2 weeks during maintenance phase

^aAll screening procedures to be performed within 14 days of start of study treatment, with the exception of CSF with positive cytology, which can be 6 weeks prior to initiation of study treatment. C1D1 and Day 1 of subsequent cycles: For C1D1 only, screening assessments may serve as day 1 assessments, except serum pregnancy (within 72 hours of drug) and except in the event that there are any indications that the participant's condition is deteriorating for which laboratory evaluations should be repeated within 48 hours prior to initiation. For all subsequent cycles, required assessments should be performed within 3 days of scheduled cycle day 1.

^bPhysical examination must include neurologic assessment.

^cSerum chemistries: Serum chemistry tests include albumin, amylase, lipase, BUN, creatinine, ALT, AST, LDH, serum alkaline phosphatase, direct and total bilirubin, glucose, total protein, sodium, potassium, chloride, HCO₃, calcium, uric acid and TSH. A reflexive free T4 and free T3 will be performed reflexively for out of range TSH values. Patients should also be tested for Hepatitis B virus surface antigens (HBV sAg) and hepatitis C virus

ribonucleic acid (HCV antibodies) at screening only.

^aEKG should be obtained at baseline for screening and then as clinically indicated

^bSerum pregnancy test (women of childbearing potential) is required within 72 hours of C1D1 dose. Pregnancy will be performed every 6 weeks while on treatment, and at 30 days and 70 days post last dose of Nivolumab.

^cCerebrospinal fluid will be collected every 4 weeks during the maintenance phase to assess disease status (will be sent for cell count, protein, glucose, cytology) and 10 cc will be saved for correlative studies as described in Section 9.0

^dTissue collected as part of clinical care (e.g. from prior biopsy, craniotomy) will be collected. See Section 9 for specimen collection requirements

^eh: Off-treatment evaluation: End of treatment assessments to be performed within 7 days after last day drug administration or within 7 days after decision to end treatment. Assessments may continue for ongoing reportable adverse events. In participants who discontinue study treatment without documented disease progression, every effort should be made to continue monitoring their disease status by radiologic imaging every 6 weeks (+/- 7 days) until (1) the start of new anti-cancer treatment, (2) documented disease progression, (3) death or (4) the end of the study, whichever occurs first

^fi: Follow-up visit 1 = 30 days from the last dose +/- 7 days or coincide with the date of discontinuation (+/- 7 days) if date of discontinuation is greater than 37 days after last dose. Follow-up visit 2 (FU2) = 8-10 weeks (+/- 7 days) from follow-up visit 1. After 2 followup visits, patients will be followed with a phone call every 10-12 weeks for survival information.

^gj: Blood will be collected at screening, Day 1, then every 3 weeks during the induction phase and every 4 weeks during the maintenance phase (two 10 mL EDTA/lavender top tube) and at the end of treatment

Calendar for Nonsmall Cell Lung Cancer Histology and Head and Neck Cancer

	Pre-Study	Wk 1	Wk 2	Wk 3	Wk 4	Wk 5	Wk 6	Wk 7	Wk 8	Wk 9	Wk 10	Wk 11	Wk 12	Off Study ^h	Follow-up visits ⁱ
								To be repeated beyond 12 weeks until patient goes off study							
Ipilimumab		A						A							
Nivolumab		B		B		B		B		B		B			
Informed consent ^a	X														
Demographics ^a	X														
Medical history ^a	X														
Concurrent meds	X	X-----X													
Physical exam ^b	X	X	X	X	X	X	X	X	X	X	X	X	X	X	X
Vital signs	X	X	X	X	X	X	X	X	X	X	X	X	X	X	X
Height	X														
Weight	X	X		X		X		X		X		X		X	X
Performance status	X	X		X		X		X		X		X		X	X
CBC w/diff, pts	X	X		X		X		X		X		X		X	X
Serum chemistry ^c	X	X		X		X		X		X		X		X	X
EKG (as indicated) ^d	X														
Adverse event evaluation		X-----X										X		X	X
Tumor measurements	X	Tumor measurements are repeated every 6 weeks. Documentation (radiologic) must be provided for participants removed from study for progressive disease.												X	
Radiologic evaluation	X	Radiologic measurements should be performed every 6 weeks (Brain MRI and CT Chest/Abd/Pelvis)												X	X
B-HCG	X ^e							X							X
Cerebrospinal fluid	X ^f	X				X				X					
Blood ^g	X	X			X				X				X	X	
Archival tissue ^g	X												X		X

A: Iplimumab 1mg/kg Q6W
B: Nivolumab 3mg/kg Q2W

^aAll screening procedures to be performed within 14 days of start of study treatment, with the exception of CSF with positive cytology, which can be 6 weeks prior to initiation of study treatment. C1D1 and Day 1 of subsequent cycles: For C1D1 only, screening assessments may serve as day 1 assessments, except serum pregnancy (within 72 hours of drug) and except in the event that there are any indications that the participant's condition is deteriorating for which laboratory evaluations should be repeated within 48 hours prior to initiation. For all subsequent cycles, required assessments should be performed within 3 days of scheduled cycle day 1.

^bPhysical examination must include neurologic assessment.

^cSerum chemistries: Serum chemistry tests include albumin, amylase, lipase, BUN, creatinine, ALT, AST, LDH, serum alkaline phosphatase, direct and total bilirubin, glucose, total protein, sodium, potassium, chloride, HCO3, calcium, uric acid and TSH. A reflexive free T4 and free T3 will be performed reflexively for out of range TSH values. Patients should also be tested for Hepatitis B virus surface antigens (HBV sAg) and hepatitis C virus ribonucleic acid (HCV antibodies) at screening only.

^dEKG should be obtained at baseline for screening and then as clinically indicated

^eSerum pregnancy test (women of childbearing potential) is required within 72 hours of C1D1 dose. Pregnancy will be performed every 6 weeks while on treatment, and at 30 days and 70 days post last dose of Nivolumab.

^fCerebrospinal fluid will be collected every 4 weeks will be sent for cell count, protein, glucose, cytology) and 10cc will be saved for correlative studies as described in Section 9.0

^gTissue collected as part of clinical care (e.g. from prior biopsy, craniotomy) will be collected. See Section 9 for specimen collection

^h: Off-study evaluation: End of treatment assessments to be performed within 7 days after last day drug administration or within 7 days after decision to end treatment. Assessments may continue for ongoing reportable adverse events. In participants who discontinue study treatment without documented disease progression, every effort should be made to continue monitoring their disease status by radiologic imaging every 6 weeks (+/- 7 days) until (1) the start of new anti-cancer treatment, (2) documented disease progression, (3) death or (4) the end of the study, whichever occurs first

ⁱ: Follow-up visit 1 = 30 days from the last dose +/- 7 days or coincide with the date of discontinuation (+/- 7 days) if date of discontinuation is greater than 37 days after last dose, Follow-up visit 2 (FU2) = 8-10 weeks (+/- 7 days) from follow-up visit 1. After 2 followup visits, patients will be followed with a phone call every 10-12 weeks for survival information.

^jBlood will be collected at screening, Day 1, then every 4 weeks during the maintenance phase (two 10 mL EDTA/lavender top tube) and at the end of treatment

11. MEASUREMENT OF EFFECT

Response in the CNS and response in non-CNS sites will be evaluated and recorded separately in this trial.

11.1 Antitumor Effect – Extracranial lesion assessments

For the purposes of this study, participants should be re-evaluated for response every 6 weeks. In addition to a baseline scan, confirmatory scans should also be obtained 3 weeks following initial documentation of objective response.

Response and progression will be evaluated in this study using the new international criteria proposed by the Response Evaluation Criteria in Solid Tumors (RECIST) guideline (version 1.1) [Eur J Ca 45:228-247, 2009]. Changes in the largest diameter (unidimensional measurement) of the tumor lesions and the shortest diameter in the case of malignant lymph nodes are used in the RECIST criteria.

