11.1.4.4 Evaluation of Best Overall Response

The best overall response is the best response recorded from the start of the treatment until disease progression/recurrence (taking as reference for progressive disease the smallest measurements recorded since the treatment started). The patient's best response assignment will depend on the achievement of both measurement and confirmation criteria.

For Participants with Measurable Disease (*i.e.*, Target Disease)

Target	Non-Target	New	Overall	Best Overall Response when
--------	------------	-----	---------	----------------------------

Lesions	Lesions	Lesions	Response	Confirmation is Required*
CR	CR	No	CR	≥4 wks Confirmation**
CR	Non-CR/Non-PD	No	PR	
CR	Not evaluated	No	PR	
PR	Non-CR/Non-PD/not evaluated	No	PR	≥4 wks Confirmation**
SD	Non-CR/Non-PD/not evaluated	No	SD	Documented at least once ≥4 wks from baseline**
PD	Any	Yes or No	PD	
Any	PD***	Yes or No	PD	
Any	Any	Yes	PD	no prior SD, PR or CR

* See RECIST 1.1 manuscript for further details on what is evidence of a new lesion.
** Only for non-randomized trials with response as primary endpoint.
*** In exceptional circumstances, unequivocal progression in non-target lesions may be accepted as disease progression.

Note: Participants with a global deterioration of health status requiring discontinuation of treatment without objective evidence of disease progression at that time should be reported as “*symptomatic deterioration*.” Every effort should be made to document the objective progression even after discontinuation of treatment.

For Participants with Non-Measurable Disease (*i.e.*, Non-Target Disease)

Non-Target Lesions	New Lesions	Overall Response
CR	No	CR
Non-CR/non-PD	No	Non-CR/non-PD*
Not all evaluated	No	not evaluated
Unequivocal PD	Yes or No	PD
Any	Yes	PD

* ‘Non-CR/non-PD’ is preferred over ‘stable disease’ for non-target disease since SD is increasingly used as an endpoint for assessment of efficacy in some trials so to assign this category when no lesions can be measured is not advised

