11.2 Antitumor Effect – Intracranial lesion assessments

For the purposes of this study, participants should be re-evaluated for intracranial response every 6 weeks. In addition to a baseline scan, confirmatory scans should also be obtained at 4 weeks following initial documentation of objective response. Response and progression will be evaluated in this study using the modified RANO Response Criteria.

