11.4 Other Response Parameters

Cerebrospinal Fluid: Cerebrospinal fluid will collected as part of clinical care.

Leptomeningeal response will be defined as below:

Response	Cytologic	Neurologic	Radiographic
Complete Response	Reversion to (-) CSF cytology (or NA)	Disappearance of all disease related symptoms present prior to therapy (or NA)	Complete disappearance of all detectable radiographic EOD (or NA)
Partial Response	> 50% decrease in malignant CSF cytology	Improvement in neurologic symptoms or no worsening of symptoms	Improvement in radiographic evidence of disease. No new sites of measurable or assessable CNS disease
Stable Disease	Not fulfilling the criteria for CR or PR, but not progressive disease	Not fulfilling the criteria for CR or PR, but not progressive disease	Not fulfilling the criteria for CR, or PR but is not progressive disease
Progressive Disease	> 50% increase in malignant CSF cytology	Development of new neurologic symptoms related to neoplastic meningitis	Increase in radiographic evidence of disease. Appearance of new sites of disease.

Leptomeningeal response will be a secondary outcome.

The immune related Response Criteria (irRC) will also be used in this study to support secondary efficacy endpoints for extracranial lesions. Definitions of the immune-related Response Criteria (irRC) are below and are presented in Appendix B:

- Complete Response (CR): Disappearance of all lesions in two consecutive observations not less than 4 wk apart
- Partial Response (PR): $\geq 50\%$ decrease in tumor burden compared with baseline in two observations at least 4 wk apart
- Stable Disease (SD): 50% decrease in tumor burden compared with baseline cannot be established nor 25% increase compared with nadir
- Progressive Disease (PD): At least 25% increase in tumor burden compared with nadir (at any single time point) in two consecutive observations at least 4 wk apart

Index Lesion	Non-Index Lesion	New Measurable Lesions	New unmeasurable lesions	% change in tumor burden	Overall IR Response
CR	CR	No	No	-100%	irCR
PR	Any	Any	Any	$\geq -50\%$	irPR
PR	Any	Any	Any	$< -50\% \text{ to } < 25\%$	irSD
PR	Any	Any	Any	$\geq +25\%$	irPD
SD	Any	Any	Any	$< -50\% \text{ to } < +25\%$	irSD
SD	Any	Any	Any	$\geq +25\%$	irPD
PD	Any	Any	Any	$\geq +25\%$	irPD

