Immune-related Progressive Disease (irPD), increases in number or size of non-index lesion(s) does not constitute progressive disease unless/until Tumor Burden increases by 25% (ie, the SPD at nadir of index lesions and any new measurable lesions increases by the required amount).

Impact of New Lesions on irRC

New lesions alone do not qualify as progressive disease. However their contribution to total tumor burden is included in the SPD which in turn feeds into the irRC for tumor response. Therefore, new non-measurable lesions will not discontinue any subject from the study.

Definition of Overall Response Using irRC Will Be Based on the Following Criteria:

[figure not shown]
- Immune-related Complete Response (irCR): Complete disappearance of all tumor lesions (index and non-index), together with no new measurable or unmeasurable lesions, for at least 4 weeks from the date of documentation of irCR. All lymph nodes short axes must be < 10 mm.
- Immune-related Partial Response (irPR): The sum of the products of the 2 largest perpendicular diameters of all index lesions is measured and captured as the SPD baseline. At each subsequent tumor assessment, the sum of the products of the 2 largest perpendicular diameters of all index lesions and of new measurable lesions are added together to provide the Immune Response Sum of the Product of the Diameters (irSPD). A decrease, relative to baseline of the irSPD of 50% or greater is considered an irPR, in the absence of irCR. Must be confirmed no less than 4 weeks from the first irPR.
- Immune-related Stable Disease (irSD): irSD is defined as the failure to meet criteria for immune complete response or immune partial response, in the absence of progressive disease.
- Immune-related Progressive Disease (irPD): It is recommended in difficult cases (eg, increase in SPD or irSPD accompanied with significant individual lesion regression, “mixed response”, or in presence of stable or improving performance status/clinical condition) to confirm PD at the following tumor assessment. Any of the following will constitute progressive disease:
 - At least 25% increase in the SPD of all index lesions over nadir SPD calculated for these lesions
 - At least a 25% increase in the SPD of all index lesions and new measurable lesions
 - (irSPD) over the nadir SPD calculated for the index lesions.

PROTOCOL NUMBER:
NCI: TBD
BMS:CA209-405

TITLE: Phase II Trial of Ipilimumab and Nivolumab in Leptomeningeal Metastases from Melanoma

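### The extracranial confirmatory scan at 3 weeks comes too early to confirm an irRC response, which needs at least 4 weeks

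*Combined protocol and SAP*

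**What the plan says.** Section 11.1, on extracranial lesions, sets the routine interval, "participants should be re-evaluated for response every 6 weeks", and adds that "confirmatory scans should also be obtained 3 weeks following initial documentation of objective response". The maintenance calendar in Section 10 has a longer routine interval: "Tumor measurements are repeated every 8 weeks". Section 10 also gives study assessments a general window of 3 days either side.

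The irRC definitions are in two places. Section 11.4 defines complete response as "Disappearance of all lesions in two consecutive observations not less than 4 wk apart" and sets the same 4-week minimum for partial response, without the word consecutive. Appendix B requires a complete response to hold for at least 4 weeks from its documentation, and says of partial response: "Must be confirmed no less than 4 weeks from the first irPR".

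For RECIST, the text of Section 11.1.4.4 makes best overall response depend on confirmation as well as measurement. The complete- and partial-response rows of its table carry a 4-week confirmation entry, but the footnote to those entries reads: "Only for non-randomized trials with response as primary endpoint". Section 13.1 names survival at 3 months as the primary endpoint.

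For brain lesions, Section 11.2 says that "confirmatory scans should also be obtained at 4 weeks following initial documentation of objective response".

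**The concern.** Sections 13.1 and 13.6 report extracranial response by RECIST and by irRC, each with a 90% exact interval. Appendix B says that irRC will underlie key efficacy endpoints. A scan ordered specifically to confirm a response should meet the interval that the criteria require, and this one does not meet the irRC interval.

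Two things are at stake. First, the additional scan cannot do its job under irRC, so a response is confirmed later than it need be. Second, Section 13.6 asks for cases where RECIST and irRC disagree to be documented. If RECIST response is read as unconfirmed while irRC response is confirmed, some disagreements will come from the confirmation rule alone and not from the behavior of the tumor.

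**Working it through.** The plan states no figure to reproduce here. The check compares intervals.

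**Inputs**
- Confirmatory scan: 3 weeks = 21 days after first documented response (Section 11.1).
- Window: 3 days either side (Section 10).
- irRC minimum: 4 weeks = 28 days (Section 11.4, Appendix B).
- Routine interval: 6 weeks (Section 11.1 and the induction and lung/head-and-neck calendars) or 8 weeks (maintenance calendar).

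**Can the 3-week scan confirm an irRC response?**
- Nominal shortfall: 28 − 21 = 7 days.
- Latest day in the window: 21 + 3 = 24. Shortfall: 28 − 24 = 4 days.

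It cannot, even at the late edge of the window.

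**When can the response first be confirmed?**
- 6-week schedule: the routine scan falls 42 days after the first. With the first scan 3 days late and the second 3 days early, 42 − 6 = 36 days, which exceeds 28. The delay against a valid 4-week scan is 6 − 4 = 2 weeks.
- 8-week schedule: 56 days, and 56 − 6 = 50 at worst. The delay is 8 − 4 = 4 weeks.

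For example, a response first seen at week 6 is rescanned at week 9, could have been confirmed at week 10, and is confirmed at week 12.

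**What the extra scan does to consecutive observations (nominal dates)**

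| Routine schedule | Extra scan at | Gaps between consecutive scans | A consecutive pair at least 4 weeks apart? |
|---|---|---|---|
| 6 weeks | 3 weeks | 3 and 3 weeks | No |
| 8 weeks | 3 weeks | 3 and 5 weeks | Yes, second pair |
| 6 weeks | 4 weeks | 4 and 2 weeks | Yes, first pair |
| 8 weeks | 4 weeks | 4 and 4 weeks | Yes, first pair |

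On the 6-week schedule as written, the consecutive-observation wording for complete response in Section 11.4 is not literally met at the next routine scan. With the first scan on its planned date, an extra scan 3 days early (day 18) and a routine scan 3 days late (day 45) still leave 45 − 18 = 27 days. Partial response is unaffected, because its definition does not require the observations to be consecutive. Appendix B does not use that word for complete response either.

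**RECIST, read both ways**
- If the footnote governs, this trial needs no RECIST confirmation, because response is not the primary endpoint. The 3-week scan is then not needed for classification.
- If the sentence about confirmation criteria governs, the only interval the table gives is at least 4 weeks, and the 3-week scan is too early.

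Under neither reading does a 3-week interval confirm a response.

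**The case against.** The strongest reply is that Section 11.1 is the RECIST section, and that RECIST as footnoted imposes no 4-week rule on a trial with a survival endpoint. That stands. A reader might infer that the scan breaches RECIST as well as irRC. The documents do not support this: what they contain for RECIST is an unresolved question of whether confirmation is required at all. The binding conflict is with irRC, which has no such exemption.

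A second reply is that the response can still be confirmed. That also stands. A reader might infer that extracranial responses cannot be confirmed under this plan. In fact the next routine scan meets the 4-week minimum for irRC partial response, and for complete response too unless the word consecutive in Section 11.4 is applied strictly.

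A third reply concerns timing tolerance. Footnotes to the Section 10 calendars allow 7 days either side, but for 6-weekly imaging after treatment stops without progression, not for confirmatory scans. Even if borrowed, that tolerance would reach day 28 only on its last day (21 + 7).

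Finally, a reader might combine the median survival of about 2–4 months in Section 13.2 with the 18 evaluable patients and infer that each responder lost to the delay costs 1/18, or 5.6 percentage points. This is not supported. Section 13.6 attaches the sample of 18 to intracranial and leptomeningeal response and gives no denominator for extracranial response, and the eligibility criteria do not require measurable extracranial disease. The survival figure describes patients in general. None is given for patients already in response.

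**Conclusion.** The inconsistency is real and sits within the documents. The scan ordered in Section 11.1 falls 7 days short of the irRC minimum, or 4 days at the late edge of the window, so it cannot confirm an irRC response. Confirmation is put off by 2 weeks on the 6-week schedule and by 4 weeks in maintenance. On nominal 6-week dates, doing the extra scan also leaves the literal complete-response wording of Section 11.4 unmet at the next routine scan.

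These conclusions assume that the 3 weeks run from the scan that first shows the response and that the general 3-day window applies. Whether RECIST response is confirmed or unconfirmed is a separate open question.

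The reach is limited to one descriptive secondary endpoint, reported with intervals and no test. The 3-month survival endpoint, the Simon design and the sample size are untouched, and no number of lost responders can be derived.

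**What to change.** 1. In Section 11.1, replace 3 weeks with at least 4 weeks, in line with Section 11.2, Section 11.4 and Appendix B. Say that the scan is not to be done before day 28; otherwise the early side of the window would allow day 25 (28 − 3) and recreate the problem.
2. In Section 11.1.4.4, state whether the RECIST response rate is confirmed or unconfirmed, and edit the table to match. If confirmation is required, remove the footnote. If it is not, remove the 4-week confirmation entries and amend the sentence that makes best response depend on confirmation. Deleting the footnote without that decision would make confirmation mandatory by default, and would also activate the 4-week condition on stable disease that carries the same mark.

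The cost is protocol wording. The number of scans stays the same, with the confirmatory scan one week later. On the 3-weekly induction schedule, a scan 3 weeks after a week-7 assessment coincides with the week-10 dosing visit, whereas a 4-week scan falls in week 11, away from dosing. The induction calendar already lists a physical examination every week, so this need not mean an extra attendance.
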